6.5.2. Laboratory Data

All relevant laboratory tests will be summarized. These summaries include categorical tables (eg, normal, high, low), and descriptive statistics for change or percent change from baseline by treatment group and visit. These laboratory tests may include the following but are not limited to this list: hematology (including TBNK and coagulation Panel), blood chemistry,

urinalysis, liver function assessment, etc. Participants who meet clinically significant categories or defined abnormal ranges as defined by laboratory will also be summarizd.

6.5.3. Vital Signs

Absolute values and changes from baseline in systolic and diastolic BP and pulse rate will be summarized by treatment group and time post-dose in accordance with the CaPS. The number and percent of participants with clinically significant change from baseline will be tabulated by treatment group.

6.5.4. Electrocardiograms

Changes from baseline for the ECG parameters QT interval, heart rate, QTc interval, PR interval, and QRS complex will be summarized by treatment and time.

Changes from baseline for the ECG parameters HR, QTcF, PR interval, and QRS complex will be summarized by treatment and time. The frequency of uncorrected QT values above 500 ms will be tabulated.

The number (%) of participants with maximum post-dose QTcF values and maximum increases from baseline in the following categories will be tabulated by treatment.

 Table 6.
 Safety QTcF Assessment

Degree of Prolongation	Mild (ms)	Moderate (ms)	Severe (ms)
Absolute value	>450 – 480	>480 - 500	>500
Increase from baseline		30-60	>60

6.5.5. Physical Examination

This is not applicable as physical examination is not collected in the study database.

6.5.6. Protocol Deviations and COVID-19 Related Reporting

In order to describe the impact of COVID-19, participants who discontinue from the study due to COVID-19 as the primary reason will be summarized in the disposition table (Section 6.4.2). The specific reasons for participants who discontinue from the study due to COVID-19, if collected in detail, such as participant decision, participant self-isolation, non-compliance with protocol, transportation issue, site restrictions, physician decision, site closed, lack of drug at site, sponsor decision, and severity of COVID-19 infection will be presented in the disposition listing.

The number and percentage of participants with at least one important PD and with at least one PD associated with COVID-19 will be summarized for the Part 1 DB phase by treatment group, deviation category, and deviation sub-category using the FAS. Important PDs and PDs related to COVID-19 will be summarized similarly overall using the FAS. This is also performed similarly for Part 1 OLE phase and Part 2 OL Safety phase.

A listing of all PDs will be provided. Important PDs and COVID-19 related PDs will be flagged in this listing for the Part 1 DB phase, Part 1 OLE phase, and Part 2 OL Safety phase.

7. INTERIM ANALYSES

An interim analysis (IA) will be conducted by the Sponsor in an unblinded manner to assess efficacy and safety after all applicable Part 1 participants complete or discontinue from study prior to the 16-week DB treatment period. The IA results will be used for decisions regarding stopping for futility and internal program development. Study conduct, including Part 1 participant continuation in OLE, will continue while the data are prepared and analyzed for the IA. The Part 2 enrollment will not be triggered until after IA shows an acceptable safety and efficacy of etrasimod 2 mg QD in the target population. Based on the IA results, the study may continue, or the study may be terminated early.

Specifically, the scope of this IA includes the following. When all applicable Part 1 participants have completed the 16-week DB treatment phase, an interim datacut will be performed that will include all efficacy and safety data up to Week 16 visit. After data cleaning is performed, unblinding of Part 1 DB treatment assignments will take place, and interim database will be released for the IA to be performed by the Sponsor and the study team. Investigators and other site staff will remain blinded during the OLE to participants' treatment assignment received in the Part 1 DB phase until the end of Part 1 OLE. Efficacy data summary will include the assessment of primary efficacy endpoint, secondary efficacy endpoints, and exploratory efficacy endpoints for Part 1 DB (Section 2.2) using the prespecified statistical methodologies (Section 5) to perform all relevant analyses described for Part 1 DB including subgroup analysis (Section 6.3). Safety data summary will include the assessment of all relevant safety endpoints (Section 3.5) descriptively summarized up to end of Part 1 DB phase.

Prior to this formal Part 1 DB IA, Sponsor may perform earlier unblinded interim analyses to inform internal decision-making regarding the development program. These earlier interim analyses will be conducted and reviewed by a limited number of team members independent of the study team. Details on these earlier unblinded interim analyses will be described in an unblinding operational plan.

When Part 1 OLE treatment phase is completed, the final analysis will be performed based on the final released official database for Part 1 of this study. This final analysis of Part 1 will include repeating the IA for Part 1 DB phase using this final data, as well as cumulative analyses including the final data from the Part 1 OLE phase. There will be no IA planned for Part 2 OL Safety phase of this study. When Part 2 OL Safety treatment phase is completed, the final analysis will be performed based on the final released official database for Part 2 of this study.

The e-DMC will be responsible for ongoing monitoring of the safety of participants in the study according to the charter. The recommendations made by the e-DMC to alter the conduct of the study will be forwarded to Pfizer for final decision. Information about the e-DMC can be found in the e-DMC Charter, which outlines the operating procedures of the

committee, including specific description of the scope of their responsibilities, including a plan where communication timelines are defined.

9. APPENDICES

Appendix 1. Summary of Efficacy Analyses

Table 7. Table of Efficacy Analyses

Endpoint Type	Estimand	FAS	Part 1 DB Phase	Part 1 DB + OLE Phase	Part 2 OL Safety
Binary Endpoints	Estimand E1 (Pre-Intercurrent Event Data)	FAS for Estimand E1	Method: CMH method adjusting to actual stratification factor of IGA score (3 or 4), MR=NR • IGA Response at Week 16 (Primary Endpoint), participants with baseline IGA ≥2 • EASI-75 Response at Week 16 (Secondary Endpoint) • IGA Response at all timepoints except Week 16, participants with baseline IGA ≥2 • EASI-75 Response at all timepoints except Week 16 • ≥4-point reduction from baseline in PP-NRS at all timepoint, participants with baseline PP-NRS ≥4 • ≥4-point reduction from baseline in Skin Pain NRS at all timepoints, participants with baseline Skin Pain NRS at all timepoints • ≥4-point reduction from baseline in Skin Pain NRS ≥4 • EASI-90 Repsonse at all timepoints • ≥4-point reduction from baseline in POEM at Week 16, participants with baseline POEM ≥4	The analyses for Part 1 DB Phase will be repeated using Part 1 final database.	None

Table 7. Table of Efficacy Analyses

Endpoint Type	Estimand	FAS	Part 1 DB Phase	Part 1 DB + OLE Phase	Part 2 OL Safety
	Estimand E1a (All Data)	FAS for Estimand E1a	Method: CMH method adjusting to actual stratification factor of IGA score (3 or 4), MR=NR • IGA Response at Week 16 (Primary Endpoint), participants with baseline IGA ≥2 • IGA Response at all timepoints except Week 16, participants with baseline IGA ≥2 • EASI-75 Response at Week 16 (Secondary Endpoint) • EASI-75 Response at all timepoints except Week 16	The analyses for Part 1 DB Phase will be repeated using Part 1 final database.	None
	No Estimand (All data)	FAS	None	 Method: CMH method adjusting to actual stratification factor of IGA score (3 or 4), MR=NR EASI-75 Response at all timepoints IGA of clear (0) or almost clear (1) based on 5-point scale at all timepoints ≥4-point reduction from baseline in PP-NRS at all timepoints, participants with baseline PP-NRS ≥4 ≥4-point reduction from baseline in Skin Pain NRS at all timepoints, participants with baseline Skin Pain NRS at all timepoints, participants with baseline Skin Pain NRS ≥4 EASI-90 Repsonse at all timepoints 	 Method: Descriptive summary using observed data EASI-75 Response at all timepoints IGA of clear (0) or almost clear (1) based on 5-point scale at all timepoints ≥4-point reduction from baseline in PP-NRS at all timepoints. participants with baseline PP-NRS ≥4 ≥4-point reduction from baseline in Skin Pain NRS at all timepoints, participants with baseline Skin Pain NRS ≥4 EASI-90 Repsonse at all timepoints

Table 7. Table of Efficacy Analyses

Endpoint Type	Estimand	FAS	Part 1 DB Phase	Part 1 DB + OLE Phase	Part 2 OL Safety
	Estimand E2 (Pre-Intercurrent Event Data)	FAS for Estimand E2	Method: JTC method via multiple imputations of missing data including data up to Week 16 Percent change from baseline in EASI score at Week 16 (Secondary Endpoint) Percent change from baseline in EASI score at all timepoints except Week 16	The analyses for Part 1 DB Phase will be repeated using Part 1 final database.	None
	Estimand E2a (All Data)	FAS for Estimand E2a	Method: MMRM without imputation of missing data including data up to Week 16 Percent change from baseline in EASI score at Week 16 (Secondary Endpoint) Percent change from baseline in EASI score at all timepoints except Week 16	The analyses for Part 1 DB Phase will be repeated using Part 1 final database.	
Continuous Endpoints	No Estimand (All data)	FAS	None	Method: MMRM without imputation of missing data including data at all timepoints (Report only OLE visits for Percent change from baseline in EASI score, report all visits for Change from baseline in POEM) Percent change from baseline in EASI score at all timepoints Change from baseline in POEM at Weeks 16, 32 and 68	Method: Descriptive summaries using observed data • Percent change from baseline in EASI score at all timepoints • Change from baseline in POEM at Weeks 24 and 52

Appendix 2. Data Derivation Details

Appendix 2.1. Definition and Use of Analysis Visit Windows in Reporting

There are two sets of analysis visit windows, one set for Part 1 (both DB and OLE phases) and another set for Part 2 (OL). For reporting purposes, the analysis visit windows will be used for efficacy and safety display that show by scheduled visits. Observations from all visits including scheduled, unscheduled and early termination visits will all be eligible for allocation to an analysis visit. If two or more observations fall into the same visit window, the observation closest to the target day will be used in the analysis. If there is a tie, the later observation will be used. However, for a participant who discontinues from the study early prior to Week 68 visit window in Part 1 (similarly to Week 52 visit window in Part 2), if two or more observations fall in the same visit window prior to Week 68 in Part 1 (similarly to Week 52 in Part 2), then the latest observation (rather than the observation closest to the target day) within this visit window will be used in the analysis for that visit window.

The analysis visit windowing will be applied after intercurrent events (initation of prohibited medications or discontinuation of study treatment, whichever is earlier) have been accounted for, that is, to the pre-intercurrent-event data and to all data separately (Appendix 3).

Table 8. Analysis Visit Windows for Part 1

Visit Label	Target Day ^a	Window Definition
Baseline	Day 1	Last non-missing assessment on or before Day 1 and prior to first dose of investigational product (ie, etrasimod or placebo)
Week 4	Day 29	Day 2 to Day 42
Week 8	Day 57	Day 43 to Day 70
Week 12	Day 85	Day 71 to Day 98
Week 16 ^b	Day 113	Day 99 to [Treatment Switch Day ^c or Day 126, whichever is smaller]
Week 20	Day 141	[Treatment Switch Day ^c +1 or Day 127, whichever is smaller] to Day 154
Week 24	Day 169	Day 155 to Day 196
Week 32	Day 225	Day 197 to Day 252
Week 40	Day 281	Day 253 to Day 322
Week 52	Day 365	Day 323 to Day 420
Week 68	Day 477	≥ Day 421

a. Target day is equal to the target week \times 7 days + 1 day.

b. All data collected on Week 16 visit, first open-label dose day (treatment switch day), will be included in ≤ Week 16 except for AE data, which will be included in ≥ Week 20. Any new treatment-emergent AE occurred on the day of first open-label dose (treatment switch day) will be included in ≥ Week 20.

c. Day of first open-label dose at Week 16 = Treatment switch day (ie, treatment switch day = treatment switch date – date of the first dose +1), where treatment switch date is taken from the Treatment Dosing CRF, as the start date in the first entry of the Treatment Dosing log for the period of Week 16 to Week 20.

Note that the upper limit of the Week 16 visit window and the lower limit of the Week 20 visit window are defined uniquely for each of the participants in the study regardless of which treatment group the participants are randomized to.

If treatment switch day (ie, day of first open-label etrasimod dose) falls between Day 99 and Day 126, then the upper limit of the Week 16 visit window is the smaller of treatment switch day or Day 126, and the lower limit of the Week 20 visit window is the smaller of treatment switch day+1 or Day 127.

In the unlikely case if treatment switch day < Day 99, > Day126, or missing (eg, discontinuation of study treatment or study prior to Week 16), then the upper limit of the Week 16 visit window will be set to Day 126 and the lower limit of the Week 20 visit window will be set to Day 127.

Table 9. Analysis Visit Windows for Part 2

Visit Label	Target Day ^a	Window Definition
Baseline	Day 1	Last non-missing assessment on or before Day 1 and prior to first dose of etrasimod
Week 4	Day 29	Day 2 to Day 42
Week 8	Day 57	Day 43 to Day 84
Week 16	Day 113	Day 85 to Day 140
Week 24	Day 169	Day 141 to Day 210
Week 36	Day 253	Day 211 to Day 280
Week 44	Day 309	Day 281 to Day 336
Week 52	Day 365	≥ Day 337

a. Target day is equal to the target week \times 7 days + 1 day.

For safety data collected for participants who complete the 2-week and 4-week follow-up visits (Weeks 70 and 72 in Part 1 OLE, Weeks 54 and 56 in Part 2 OL Safety phase), available safety data will be summarized for these nominal visits.

For 12-Lead ECG collected on Day 1 during first-dose cardiac monitoring, the labels for timepoints can be "Day 1 Predose", "Day 1 1HR Postdose" to "Day 1 4HR Postdose".

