8.3.2. Vital Signs

Resting vital signs measurements will be made in the seated position and include pulse rate, blood pressure, body temperature, and respiratory rate. Pulse rate will be collected as part of vital signs and heart rate will be collected as part of the ECG. Vital signs will be measured prior to any blood draws that occur within the same collection window. Vital signs will be collected at timepoints specified in the SoA. See Section 10.10.3.1.2 for first dose cardiac monitoring details. If the first reading is abnormal for any parameters, they may be repeated up to 2 times during a visit (only applicable to first dose cardiac monitoring or cardiac monitoring during the treatment reinitiation following the defined periods of treatment interruption).

Any untoward vital sign findings that are identified during the active collection period and meet the definition of an AE or SAE (Appendix 3) must be reported according to the processes in Sections 8.4.1 to 8.4.3.

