8.3.6. Clinical Safety Laboratory Assessments

See Appendix 2 for the list of clinical safety laboratory tests to be performed and the SoA for the timing and frequency. All protocol-required laboratory assessments, as defined in Appendix 2, must be conducted in accordance with the laboratory manual and the SoA. Unscheduled clinical laboratory measurements may be obtained at any time during the study to assess any perceived safety issues.

The investigator must review the laboratory report, document this review, and record any clinically significant changes occurring during the study in the AE section of the CRF. Clinically significant abnormal laboratory test findings are those that are not associated with the underlying disease, unless judged by the investigator to be more severe than expected for the participant's condition.

All laboratory tests with values considered clinically significant and abnormal during participation in the study or within 28 days after the last dose of study intervention should be repeated until the values return to normal or baseline or are no longer considered clinically significant by the investigator or study medical monitor.

If such values do not return to normal/baseline within a period of time judged reasonable by the investigator, the etiology should be identified and the sponsor notified.

See Section 10.5 for suggested actions and follow-up assessments in the event of potential DILI.

See Section 10.6 for instructions for laboratory testing to monitor kidney function and reporting laboratory test abnormalities.

For laboratory collection volumes, see the laboratory manual.

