10.10.3. First-Dose Cardiac Monitoring

Cardiac monitoring following treatment initiation applies to the first dose administered in the Treatment Period (Day 1). Day 1 predose (ie, Baseline) vital signs (resting HR, BP, body temperature, and respiratory rate) will be used as the baseline measurements. The lowest predose HR measurement (by vital signs) will be used for comparison to the postdose measurement. It should be noted that in this section heart rate refers to pulse rate. Pulse rate will be collected as part of vital signs and heart rate will be collected as part of the ECG.

Cardiac monitoring is required at the Day 1 (first blinded dose) of Part 1 and Part 2 and Week 16 (first open label etrasimod dose) of Part 1 and will also be necessary to reinitiate study treatment if consecutive days of study treatment are missed as described in Section 7.1.7. These visits for cardiac monitoring should be conducted in the morning and not on a Friday or the day before a site-observed holiday. In the following sections describing first-dose cardiac monitoring, Day 1 refers to the first day of treatment in the Treatment Period, but the same procedures will also be used at the Week 16 visit in Part 1 (first open label dose) and the first day of treatment re-initiation following the defined periods of treatment interruption noted above. Day 2 refers to the subsequent dosing day.

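### The SAP's visit-window rule lets abnormality-triggered repeats displace scheduled values in by-visit safety displays, and the SAP does not say which observations feed the laboratory and vital-sign incidence summaries

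*SAP*

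**What the plan says.** SAP Appendix 2.1 covers safety explicitly: "the analysis visit windows will be used for efficacy and safety display that show by scheduled visits". On eligibility it says: "Observations from all visits including scheduled, unscheduled and early termination visits will all be eligible for allocation to an analysis visit". When several values share a window, "the observation closest to the target day will be used in the analysis", and then: "If there is a tie, the later observation will be used". For a participant who leaves the study before the Week 68 window (Part 1) or the Week 52 window (Part 2), if several values fall in one earlier window, "then the latest observation (rather than the observation closest to the target day) within this visit window will be used". The appendix gives no priority to the scheduled value and does not keep the worst one.

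The protocol ties repeats to abnormality:

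- **Laboratory, Protocol 8.3.6:** clinically significant abnormal values "should be repeated until the values return to normal or baseline or are no longer considered clinically significant".
- **Blood counts, Protocol 10.10.1:** the CBC is repeated weekly after an ANC below 1.0 × 10⁹/L or a WBC count above 20 × 10⁹/L.
- **Vital signs, Protocol 8.3.2:** "If the first reading is abnormal for any parameters, they may be repeated up to 2 times during a visit", but only during cardiac monitoring at first dose or at re-initiation.

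SAP 6.5.4 uses the maximum post-dose value for QTcF. SAP 6.5.2 (laboratory) and 6.5.3 (vital signs) promise summaries of participants with clinically significant findings without naming the observations used. SAP 3.1 makes the incidence of such changes a primary endpoint for the Part 1 OLE and Part 2.

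**The concern.** A closest-to-target rule is harmless when extra observations arise for reasons unrelated to their values. Here they do not. A normal laboratory result generates no repeat, while a clinically significant one generates repeats until it settles. Letting the repeat compete with the scheduled value means that selection depends on the outcome, and it works in one direction. A group with more abnormal values has more of them open to displacement, so a between-arm contrast in the double-blind phase can be narrowed as well as the levels lowered.

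The displays exposed are the by-visit laboratory categories and changes from baseline in SAP 6.5.2. The second issue is the silence on incidence. If a programmer builds those tables from the windowed records, the same selection reaches a primary safety endpoint.

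**Working it through.** **1. The plan's own figures.** Target day = 7 × week + 1. Week 16 gives 113, Week 24 gives 169 and Week 68 gives 477. Every entry in SAP Tables 8 and 9 is reproduced.

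**2. Inputs.** Visit tolerance W is ±5 days up to Week 20 in Part 1 and up to Week 16 in Part 2, and ±7 days from Week 24 (Schedule of Activities). Let x be the scheduled visit's offset from target in days, and g the days from the abnormal value to its repeat. The documents give neither the spread of x nor, apart from the weekly CBC, the gap g. I assume x is even over the allowed days and show a range of g.

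**3. Condition for displacement in participants who stay in the study.** The repeat is used if |x + g| ≤ |x|. For g ≥ 1 this needs x < 0 and g ≤ 2|x|. The number of allowed days that qualify is W − ⌈g/2⌉ + 1 (zero if negative), out of 2W + 1.

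| Gap g (days) | ±5 days | ±7 days |
|---|---|---|
| 0 (same day, always a tie) | 11/11 = 100% | 15/15 = 100% |
| 1 or 2 | 5/11 = 45% | 7/15 = 47% |
| 3 | 4/11 = 36% | 6/15 = 40% |
| 5 | 3/11 = 27% | 5/15 = 33% |
| 7 | 2/11 = 18% | 4/15 = 27% |
| 10 | 1/11 = 9% | 3/15 = 20% |
| 14 | 0 | 1/15 = 7% |
| 15 | 0 | 0 |

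Example: Week 24, target Day 169. A visit on Day 165 (x = −4) with a repeat on Day 172 (x + g = +3) loses its scheduled value, since 3 ≤ 4. A visit on Day 169 with a repeat on Day 176 keeps it, since 7 > 0. A visit on or after target is never displaced by a later-day repeat.

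**4. Does the repeat stay in the window?** A displacing repeat lies at most W days after target. The Week 4, 8, 12 and 20 windows in Table 8 run 13 days past target (for example 42 − 29 = 13), and the Week 24 window runs 196 − 169 = 27, so nothing is cut off. Week 16 is the exception. If the switch to open label falls on Days 99-126, the window closes on the switch day. A repeat after that day goes to Week 20 and cannot displace Week 16. Nor would it normally displace Week 20: a repeat on Day 120 is 141 − 120 = 21 days from target, against at most 5 for an on-time visit.

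**5. Early leavers.** The latest value in the window wins whatever its distance, so any later repeat in the same window displaces the scheduled value: 100%.

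**6. Vital signs.** Abnormality-triggered repeats occur only in cardiac monitoring: Day 1, Part 1 Week 16 and re-initiation. Table 8 takes baseline before the first dose and starts the Week 4 window on Day 2, so Day 1 post-dose readings fall in no post-baseline window. Footnote b of Table 8 keeps non-AE data from the switch day at or before Week 16. The tie rule therefore reaches vital signs only at Part 1 Week 16 and at re-initiation visits.

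**7. Incidence summaries.** QTcF: maximum post-dose value stated. Laboratory and vital signs: not stated.

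**The case against.** The case against is substantial, and most of it limits the size.

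- Closest-to-target with a tie-break is a reproducible convention for descriptive tables, and preferring the scheduled value is partly a matter of choice. That holds where extra values arise independently of the result. It does not hold for repeats triggered by abnormality.
- Later-day repeats leave the scheduled value in place on more than half of the allowed visit days. This stands for participants who stay in the study.
- A repeat need not be normal. This stands: displacement moves the display toward the repeat, which is toward normal only to the extent that the value has recovered.
- Sites are blinded to WBC, differential and TBNK results. Protocol 10.10.1 has investigators notified of Grade 4 lymphopenia, low ANC or high WBC, so ordinary lymphocyte falls should not generate site repeats. This stands and protects the drug's main laboratory effect.
- Safety summaries follow sponsor standards that are not in these documents and may settle the incidence question. That is possible, but the SAP settled it for QTcF and should do so here.

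Two stronger readings are tempting. A reader might infer that abnormal values vanish from the safety report. They do not: clinically significant laboratory changes are also recorded as AEs (Protocol 8.3.6), and the participant-level summaries in SAP 6.5.2 and 6.5.3 are not described as windowed.

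A reader might also infer that first-dose bradycardia is understated. Step 6 shows that the tie rule does not reach Day 1 post-dose readings, and SAP 6.5.3 summarises vital signs by time after dosing. The different predose comparator in Protocol 10.10.3, "The lowest predose HR measurement (by vital signs) will be used for comparison to the postdose measurement", does not help that reading. With assumed predose readings of 49 then 56 and a nadir of 46, the last-value baseline in SAP Table 8 gives a fall of 56 − 46 = 10 bpm, against 49 − 46 = 3 bpm. The SAP shows the larger fall, and the protocol comparator belongs to the bedside monitoring procedure.

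**Conclusion.** The concern holds in a limited form. The window rule can shift by-visit laboratory displays toward normal. Displacement is certain for early leavers with a later repeat in the window, who may include participants stopped for safety, and for same-day repeats in a post-baseline window. For other participants it is 36-40% of visit days at a 3-day gap and 18-27% at 7 days. It is zero for visits on or after target with a later-day repeat, and at Week 16 for repeats after a switch on Days 99-126.

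These shares assume visits spread evenly over the allowed days, and they apply only once a repeat has been taken. The documents do not give the frequency of repeats or how far values recover, so the shift in any table's percentages cannot be computed.

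The gap in SAP 6.5.2 and 6.5.3 needs no assumption: the observations behind a primary safety endpoint are not specified.

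**What to change.** Add a safety-specific selection rule to SAP Appendix 2.1, with a cross-reference from 6.5.2 and 6.5.3, before the interim database is released:

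- **By-visit displays:** use the scheduled value (for vital signs, the first reading at the nominal timepoint). Use an unscheduled or repeat value only when the scheduled one is missing. Apply this to early leavers too, in place of the latest-value clause.
- **Incidence tables** of abnormal or clinically significant laboratory and vital-sign values: use all post-baseline values, including repeats and unscheduled ones, and retain the worst for each participant.

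The efficacy windowing and the protocol's monitoring procedures stay as they are. The cost is SAP wording and a little programming. The downside is slightly higher displayed abnormal rates.
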